The study will be single blinded into two groups matched for age, sex and BMI in order to achieve similar weight loss in liraglutide and placebo arms. In addition to a fixed dose of metformin (2 g/day) and simvastatin (20 mg/day) treatments, patients will be assigned to liraglutide therapy once daily and randomized to liraglutide group with uncontrolled diet or to placebo group with weight loss of 3.0 kg supervised by the study dietician for 4 months (Figure 3). Previous studies in type 2 diabetes show that the average weight loss with liraglutide is 3-3.5 kg and stable weight is achieved within 3-3.5 months (LEAD1-6). The study cohort will comprise male and female (non-fertile or of child-bearing potential using a medically approved birth control method) with T2DM eligible for treatment with metformin or on stable dose of metformin.

INCLUSION CRITERIA

Obese subjects with T2D and a large waist (waist > 88 cm in women and > 92 cm in men, BMI 27–40 kg/m², triglycerides between 1.0 – 4.0 mmol/L and LDL < 4.5 mmol/l) treated with a lifestyle or metformin (any dose) (HbA1c 6.5-9%) and aged 30 – 75 years will be included. Subjects may or may not use statins. **Only subjects who sign an informed consent are included to the study.**

EXCLUSION CRITERIA

- Type 1 diabetes
- Apo E2/2 phenotype
- ALT/AST > 3x ULN
- GFR < 60 ml/min, clinically significant TSH outside normal range
- Lipid-lowering drugs other than statins within 6 months
- Treatment with pioglitazone, insulin, sulphonylureas, gliptines, glinides, SGLT-2 inhibitors or thiazide diuretics (at a dose of > 25 mg / day) within 6 months
- Blood pressure > 160 mmHg systolic and/or > 105 diastolic
- History of pancreatitis or stomach / other major bleeding, thyroid neoplasia, persistent hypothyroidism or persistent hyperthyroidism
- Any medical condition that puts the patient in the risk of dehydration
- Concurrent medical condition that may interfere with the interpretation of efficacy and safety data during the study.
- Females of childbearing potential who are not using adequate contraceptive methods
- Subjects who have experienced side-effects previously from GLP-1 agonists
- Non-compliance or withdrawal of consent
- **Any information or clinical event described in liraglutide SPC that is a contraindication for the use of liraglutide (http://www.ema.europa.eu/docs/en_GB/document_library/EPAR_-_Product_Information/human/001026/WC500050017.pdf)**

WHITHDRAWAL FROM THE STUDY

- Withdrawal of consent

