- Clinical information/condition/adverse event that potentially endangers study subject/study results judged by the PI of the study
- **any information or clinical event described in liraglutide SPC that is a contraindication for the use of liraglutide (http://www.ema.europa.eu/docs/en_GB/document_library/EPAR_-_Product_Information/human/001026/WC500050017.pdf)**

Restrictions during the study:

- No aspirin and non-steroidal anti-inflammatory drugs (NSAIDs) within 1 week before heparin tests (LPL / HL) and biopsies
- No alcohol or strenuous exercise within 72 hours of each special test
- Serum amylase and lipase is followed at screening, week 8 and end of liraglutide treatment period or at clinical suspicion of pancreatitis

STUDY VISITS

All subjects will undergo a screening visit. Before screening, the subjects may visit the study center for screening laboratory tests. After giving extensive oral and written information, a written informed consent form will be obtained from the subjects at the first visit before screening procedures. Subjects will be informed on all adverse events related to all the study procedures they will be submitted to both orally and in writing.

Subjects eligible for the study will enter the run-in phase and treated with Metformin 2 g/day and Simvastatin 20 mg/day for 4 weeks. In the treatment period, subjects are randomized to Liraglutide or placebo. To keep subjects blinded, Liraglutide and placebo will be visually identical and be packed. Liraglutide and placebo will be provided by Novo Nordisk A/S. Investigators are not blinded in order to advice subjects

in placebo group to lose weight 3 kg during the study. Dose will be escalated to Liraglutide 0.6 mg / placebo 0.1 ml for one week, Liraglutide 1.2 mg/ placebo 0.2 ml one week and thereafter Liraglutide 1.8 mg / placebo 0.3 ml s.c. daily injections.

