Tracer labelling. On the evening of the first visit, $^2\text{H}_2\text{O}$ (2 g/kg) will be given between 18:00 and 22:00 to assess the contribution of de novo lipogenesis to fatty acids in VLDL (Figure 3). At 8:00 the following morning, the subjects will receive a bolus injection of $^2\text{H}_5$ -glycerol (500 mg) to assess the VLDL-triglyceride kinetics, and a bolus injection of $^2\text{H}_3$ -leucine (7 mg/kg) to assess VLDL-apoB100 and chylomicron-apoB48 kinetics. The fat rich mixed meal (57 g fat, 63 g carbohydrates and 40 g protein, total 934 kcal) with $^{13}\text{C}_4$ -palmitate tracers (1-2 g) is served 2 h after the infusions begins.

Sampling and sample preparation. Blood samples will be taken at frequent time points as indicated by the red dots (Figure 4) and lipoprotein fractions (chylomicrons, VLDL₁ and VLDL₂) will be separated by density gradient ultracentrifugation (DGU). Concentrations of lipids and apolipoproteins (apo-B100, apo-B48) will be measured in whole plasma and in all fractions at each time point.

Quantification of lipoprotein fluxes. Enrichments of isotopes in lipids (TG, FAs) and in apo-B100 and apo-B48 are determined by GC/MS [28] and/or by proteomics [29] at each time point (red dots). Hepatic DNL is calculated from enrichment of deuterated water ingested during the kinetic study at specified time points (0, 4 and 8 hrs.) [30]. We will use a novel multicompartmental model to describe the fluxes of materials combining apoB100 and apoB48 kinetics [7, 28, 29].

2. Determination of liver, subcutaneous and intra-abdominal fat. Using standardized protocols, we will perform a proton magnetic resonance spectroscopy (MRS) to determine liver fat content and magnetic resonance imaging to determine subcutaneous abdominal and intra-abdominal fat. [31]

3. Lipolytic enzymes, advanced lipid analysis, fat biopsies and genetic studies. We will analyze mass and enzyme activity of LPL and hepatic lipase after an injection of 75 IU/kg heparin. RLP-TG and RLP-cholesterol will be measured at 0, 4, and 8 hrs. A fasting sample is obtained for LDL and HDL size determination.

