The study continues until 13 subjects have completed in both arms. Subjects completing the protocol are included to the statistical analyses. Paired t-test (within group) and ancova (treatment effect) will be used. The number of subjects needed is based on previous studies and are in accordance with a recently published article showing that a 25% difference in VLDL kinetics can be detected with 9 subjects per each group [33].

PRIMARY OBJECTIVE

1) To examine the effect of 16 weeks of treatment with liraglutide on triglycerides (TG) and apoB48 production rates (PR) and/or fractional catabolic rates (FRC) in the lipoprotein fraction chylomicrons ($S_f > 400$) in patients with T2DM treated with metformin. This will be fulfilled by kinetic modeling during a standardized fat-rich mixed-meal test combined with stable isotope administration.

2) To evaluate the for the first time in humans the effect of 16 weeks of treatment with liraglutide compared to baseline on hepatic DNL and liver fat content in patients with T2DM treated with metformin, assessed during a standardized fat-rich mixed meal test.

SECONDARY OBJECTIVES

To evaluate the effect of 16 weeks of treatment with liraglutide compared to baseline in patients with T2DM treated with metformin, assessed during a standardized fat-rich mixed-meal test combined with stable isotope administration on:

- production rates (PR) of TG, apo-B48 and apo-B100 in the lipoprotein fractions VLDL₁ (Sf 60–400) and VLDL₂ (Sf 20–60)
- fractional catabolic rates (FCRs) of TG, ap-B48 and apo-B100 in the lipoprotein fraction VLDL₁ (Sf 60–400) and VLDL₂ (sf 20–60)
- fasting and postprandial serum total TG, total cholesterol, and total apo-B, apo-B48, RLP-chol and RLP-TG, apo-CIII and apo-A5 as well as fasting LDL and HDL size. RLP-chol and RLP-TG are surrogate markers of remnants. Apo-CIII and apo-A5 are key regulators of the lipolytic cascade.
- TRL clearance assessed as effect on post-heparin lipoprotein lipase (LPL) and hepatic lipase (HL) activities. LPL and HL are the key enzymes regulating lipolysis of TRLs and remnant removal by the liver.
- fasting and postprandial glucose, insulin and C-peptide, assessed also during an OGTT.
- fasting visceral and subcutaneous fat depots assessed by MRS in both fasting and in postprandial period.

SAFETY REPORTING

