Any adverse events will be reported to Finnish Medicines Agency (FIMEA) according to local procedures. All adverse events will be collected from the first study-related activity (from the signing of the informed consent) and in all following contacts with the study-subject through-out the project. This includes events from the first trial related activity after the subject has signed the informed consent, and until the post treatment follow-up period. The investigators will copy Novo Nordisk Finland Safety department when expediting to FIMEA any serious adverse reactions (SAR) or suspected unexpected serious adverse reactions (SUSAR) which occurred during the use of liraglutide in the study (**appendix B**). ***In addition, all pregnancies in trial subjects occurring during use of a Novo Nordisk Product will be reported to Novo Nordisk.*** The submission to Novo Nordisk Finland will be made within 15 days from the investigator's first knowledge about a valid case.

BUDGET

The study protocol utilizes state-of the art methods to measure the dynamics of postprandial lipemia and extensive and complex assessments (including magnetic resonance imaging/spectroscopy, biochemical and molecular analyses) all of which need to be performed by skilled personnel. We have calculated an overall budget of approximately 574 000€. The budget does not include study medication (liraglutide). The study is financed by an independent grant from Novo Nordisk Ag and by other research grants.

GENERAL CONSIDERATIONS

The clinical part of the study will be conducted in the research facilities of Research Programs' Unit, Diabetes & Obesity, University of Helsinki; Clinical Research Institute, Huch Ltd. Biomedicum Helsinki, Finland. Laboratory work and analysis will be made in Helsinki and Gothenburg centers. The study protocol will be subjected to the consideration of the Medical Ethical committee of the Helsinki University Central Hospital and permission from the Finnish Medicines Agency (Fimea) will be obtained. The study will be conducted according to GCP and GLP standards. The subjects taking part to the study are insured by a patient insurance taken out by the Helsinki University Central Hospital.

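### Investigators know the arm so that they can coach weight loss, and the available text states no masking for kinetic model fitting, sample exclusions or liver MRS processing

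*Combined protocol and SAP*

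**What the plan says.** The TREATMENT section sets the level of blinding: "The study will be single blinded into two groups matched for age, sex and BMI". STUDY VISITS explains how it is kept: "To keep subjects blinded, Liraglutide and placebo will be visually identical and be packed". The same paragraph then says "Investigators are not blinded in order to advice subjects" in the placebo group on losing 3 kg.

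The primary outcomes are derived quantities. For the first primary objective (chylomicron triglyceride and apoB48 production and/or fractional catabolic rates), PRIMARY OBJECTIVE says "This will be fulfilled by kinetic modeling during a standardized fat-rich mixed-meal test" with stable isotopes. The second concerns the "effect of 16 weeks of treatment with liraglutide compared to baseline on hepatic DNL and liver fat content".

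STUDY PROTOCOL describes the methods. On fluxes: "We will use a novel multicompartmental model to describe the fluxes of materials combining apoB100 and apoB48 kinetics". On liver fat, working to standardized protocols, "we will perform a proton magnetic resonance spectroscopy (MRS) to determine liver fat content". DNL is calculated from deuterium enrichment at 0, 4 and 8 hours. GENERAL CONSIDERATIONS adds: "Laboratory work and analysis will be made in Helsinki and Gothenburg centers".

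None of these places, nor any other part of the available text, says whether laboratory staff, modellers or MRS readers are masked to arm or visit, or whether samples and scans are coded. STUDY PROTOCOL item 1 refers to Appendix A for a detailed account of the analysis; that appendix was not available.

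**The concern.** The reason given for unblinding is specific: someone must advise placebo subjects on weight. It has no bearing on the person who judges whether a model fit is acceptable, drops an outlying sample or processes a spectrum. Those steps can be masked without touching the intervention or the coaching.

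They also involve judgement. The non-steady-state model was developed on data from 5 subjects, so its fitting conventions are young. The plan leaves open whether enrichment is measured by GC/MS, proteomics or both, and whether the first objective is met through production rates, catabolic rates or both. The hypotheses are directional, so anyone handling the data knows which way the result is expected to go.

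If fitting, exclusion and reading decisions are made with arm and visit visible, they can lean in the expected direction. More subjects would not remove such a shift, and the analysis could not detect it afterwards. For comparisons with baseline, knowledge of visit matters as much as knowledge of arm.

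**Working it through.** **What the text establishes, step by step**

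| Step | Masking stated? | Room for judgement |
|---|---|---|
| Subject | Yes, identical product | – |
| Staff who advise on weight | Expressly unblinded, with a reason | – |
| Compartmental model fit, sample exclusions | Not stated | Greatest |
| MRS liver fat | Not stated; protocols standardized | Some, in spectral processing |
| DNL from enrichment at fixed times | Not stated | Lower |

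**How large a bias would matter (illustration)**

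The documents give no estimate of assessment bias. STATISTICAL METHODS AND POWER gives 13 completers per arm and a cited 25% difference in VLDL kinetics detectable with 9 per group. It gives no alpha, sidedness, power or SD, so the plan's own sample-size figure cannot be reproduced. It can only be solved backwards under assumptions.

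1. Assume a two-sided 5% two-sample t-test with 80% power. With 9 per group (16 df), the noncentral t gives a detectable standardized difference of 1.407.
2. Implied SD = 25 / 1.407 = 17.8% of the mean.
3. Standard error of the between-arm difference with 13 per arm: SE = SD × √(2/13). This is 6.97 points at SD 17.8%, 9.81 at SD 25% and 15.69 at SD 40%. The last two SDs are assumed, to show the range.
4. With no true effect and a systematic shift b, the t statistic is noncentral with 24 df and noncentrality b/SE. The false-positive rate is P(|t| > 2.064). Example: b = 5 at SD 17.8% gives 5/6.97 = 0.717 and a rate of 10.6%.

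| Assumed shift (points) | SD 17.8% | SD 25% | SD 40% |
|---|---|---|---|
| 0 | 5.0% | 5.0% | 5.0% |
| 3 | 7.0% | 6.0% | 5.4% |
| 5 | 10.6% | 7.8% | 6.1% |
| 10 | 28.1% | 16.5% | 9.4% |

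The shifts are assumptions with no source in the documents. The 17.8% is back-solved from VLDL kinetics and need not apply to chylomicron kinetics or liver fat. The plan uses ANCOVA between groups and paired t-tests within groups, whereas the table uses an unadjusted two-sample test. If baseline adjustment reduces the residual SD, the same shift has a larger effect.

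**The case against.** **Silence is not evidence of unmasked reading.** This stands. Appendix A is where coding of samples or the conduct of modelling might be described. A reader might infer that the modellers and MRS readers know the arm. The documents do not say so; they show only that no masking is stated in the available text.

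**The unblinding sentence is about people who advise subjects.** This stands too. A reader might take it to unblind everyone on the study team, but its purpose clause points to coaching staff and the other roles are not mentioned. The gap is that the sentence sets no limit and nothing else fills it.

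**Other protections exist.** Randomization, identical product and standardized imaging protocols all help, and prespecified fitting and exclusion rules would help further. It would be wrong to call masked assessment the only safeguard. But randomization and identical product do not act on the assessor, and a standardized protocol fixes the method without hiding the arm.

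**Subject blinding may be better than it looks.** The 3 kg target applies only to placebo, which could suggest that subjects can easily guess their arm. However, STUDY VISITS has subjects meet the dietician after randomization and receive weekly weight and diet contacts, without restricting either to placebo. The point here does not depend on subjects guessing.

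**Two centres may mean separate teams.** The documents name Helsinki and Gothenburg for laboratory work and analysis, but Helsinki is also the clinical site. Nothing says who fits the model or reads the scans, so independence cannot be assumed.

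**The figures are illustrative.** Agreed. The 28% holds only for a 10-point shift at the smallest of the three SDs. At SD 40% the same shift gives 9.4%, and a 3-point shift changes little at any of them.

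**Conclusion.** The point holds as a risk of bias that the plan could remove cheaply. The coaching reason does not require the kinetic modelling, sample exclusions or liver MRS processing to be unmasked, and the available text states no masking for them. Exposure is greatest for chylomicron triglyceride and apoB48 production and catabolic rates, present for MRS liver fat, and lower for DNL.

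The size cannot be fixed from the documents. Under the stated assumptions, false-positive rates run from about 5% (3-point shift, SD 40%) to about 28% (10-point shift, SD 17.8%). No bias has been shown to occur, and the table should not be read as a forecast. The conclusion is conditional on Appendix A not already providing masked assessment.

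**What to change.** - In STUDY VISITS, limit unblinding to the staff who coach and follow subjects.
- In STUDY PROTOCOL (items 1 and 2), state that plasma fractions, enrichment datasets and MRS/MRI files carry a code that hides arm and, where possible, visit.
- In the same place, state that model fitting, sample exclusions, DNL calculation and MRS/MRI reading are completed and locked before the code is broken.
- If Appendix A already says this, cross-refer to it from both sections.

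The cost is minor logistics for coding samples and files. No extra reader is needed, because a coded file masks even a person who has another role in the study. Sample size, intervention and coaching stay as they are. The change must be made before the data are read, since masking cannot be restored afterwards.

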Thereafter the baseline visits will include an OGTT, heparin test, non-fasting kinetics and abdominal MRI investigation days. The investigational product (Liraglutide or placebo) will be given to the subjects together with detailed instructions about the usage and storage (**Shelf life 30 months. After first use: 1 month. Storage in a refrigerator (2°C - 8°C). Do not freeze. Store away from the freezer compartment.**) (in +2 - +8 degrees, opened product in +2 - +29 degrees) of the product during these visits. After the study period of total 4 months these investigations are repeated. In addition to the screening visit(s), the subjects will undergo 8 investigational visits. The subjects meet dietician after randomization. The follow-up about weight, diet and possible adverse events takes place with weekly phone calls/e-mail contacts by the study nurse/dietician/doctor. Subjects fill in dietary records for 3 days before and during the investigational drug. At week 8 after initiation of the treatment period a blood sample for safety is drawn, weight is recorded and the patient meets dietician/study nurse if necessary. In case of unsuccessful weight loss, weight loss > 1.5 kg/month or adverse events, an additional visit is arranged. The duration of the study is 1-1.5 month run in and 4 to 4.5 month investigational phase i.e. 5 to 6 months. The subjects will be followed by a phone call/e-mail/visit 2 weeks after the end of the treatment period.

STUDY PROTOCOL: We will combine the novel kinetic protocol developed by us with several advanced analyses to elucidate how incretins modulate postprandial lipidemia and hepatic DNL in T2D subjects. To specifically elucidate the impact of a GLP-1 agonist on postprandial lipid metabolism, we will perform kinetic studies on all study subjects before and after the 4-months intervention with the GLP-1 agonist.

[figure not shown]

Figure 4. Detailed schedule for lipoprotein kinetic assessment. Red dots represent plasma samples for kinetic data (glycerol, leucine and palmitate enrichment in TRL fractions) and green arrows illustrate time-points for plasma incretin (GLP-1, GIP), glucose and insulin sampling.

1. Kinetic study with stable isotopes combined with an oral fat load. This study is based on the novel protocol developed by us (Figure 4). A detailed description of analysis is given in **Appendix A**.

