4. Oral glucose tolerance test. An oral glucose tolerance test will be performed as indicated after overnight fast at screening and the end of the 4 months intervention with the GLP-1 agonist. Glucose and insulin will be measured at 0,5,10,30,60,90,120,180 and 240 minutes and modeling of β -cell function is performed [32]. Samples of markers of energy balance (FFA, β -OHB) will be taken at three time-points (0, 4, and 8hrs) after the oral fat load.

OPTIONAL ANALYSES FOR THE FUTURE STUDIES

1. Advanced lipid analysis, fat biopsies and genetic studies

We will also utilize this protocol to collect material for optional analyses in the future not covered by this budget. We will perform lipidomics profiling of plasma and isolated lipoproteins by GC/MS technology to map lipids and proinflammatory lipid intermediates (with collaborators of principal instigators [name] and [name]). We will obtain needle biopsies of subcutaneous abdominal fat after fasting to measure mRNA levels of proinflammatory cytokines and biomarkers and to analyze lipids in adipose tissue. We will also take a blood sample for DNA extraction and identify common single nucleotide polymorphisms in genes that have been verified to play a role in lipid metabolism, insulin resistance, inflammation or oxidative stress

2. Analysis of biomarkers during the oral fat load; apo-CIII, apo-A5, uric acid, inflammatory biomarkers (hsCRP, TNF- α , IL-6, SAA, IL-8, PON, MPO, MCP-1) and PAI-1 at three time-points (0, 4, and 8hrs) after the oral fat load. Spare samples of plasma/serum for future angiopoietin-like protein 4 and other lipid/metabolic parameters is stored at -80 degrees at all time-points during fat rich meal test and OGTT.

3. Analysis of gut microbiome profile and urine microvesicles. Because obesity and diabetes may induce low-grade inflammation and insulin resistance due to changes in gut microbial community, the subjects will also provide a stool sample (using specific tubes and instructions) for analysis of gut microbiota profile before and after liraglutide treatment. A urinary sample for selective purification of nucleic acids and proteins that are potential markers of metabolic state and chronic diseases.

STATISTICAL METHODS AND POWER

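### The first OGTT is placed at screening in one section and at the post-run-in baseline visits in another; a screening baseline would put run-in change into the within-group OGTT results

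*Combined protocol and SAP*

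**What the plan says.** Item 4 of the section headed Study Protocol states that the OGTT is "performed as indicated after overnight fast at screening and the end of the 4 months intervention with the GLP-1 agonist". Glucose and insulin are measured over 240 minutes and beta-cell function is modelled from them.

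The Study Visits section gives a different schedule. Eligible subjects first go through a run-in: "Subjects eligible for the study will enter the run-in phase and treated with Metformin 2 g/day and Simvastatin 20 mg/day for 4 weeks". On the baseline assessments it says: "Thereafter the baseline visits will include an OGTT, heparin test, non-fasting kinetics and abdominal MRI investigation days". Study product is handed out during these visits. It continues: "After the study period of total 4 months these investigations are repeated", and "In addition to the screening visit(s), the subjects will undergo 8 investigational visits". The overall timing is: "The duration of the study is 1-1.5 month run in and 4 to 4.5 month investigational phase i.e. 5 to 6 months".

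The Inclusion Criteria admit subjects treated by lifestyle alone or with metformin at any dose. The Secondary Objectives compare 16 weeks of liraglutide with baseline in metformin-treated patients, and list glucose, insulin and C-peptide, including during an OGTT. The analysis rule in Statistical Methods and Power is: "Paired t-test (within group) and ancova (treatment effect) will be used". No sentence says which OGTT supplies the baseline value.

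**The concern.** Screening and the baseline visits are different occasions in this protocol, and the run-in appears to lie between them. A subject who enters on lifestyle alone starts metformin in that interval. One on a lower dose is moved to the fixed dose. One already on that dose has no change in metformin. The shift in glucose-lowering background therefore differs between subjects, and OGTT glucose, insulin and the derived beta-cell measures are outcomes it can move.

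If item 4 is followed and the screening test serves as baseline, each within-group change is the sum of a run-in change and a treatment-period change. The paired t-test cannot separate them, so a response to background metformin could be reported as an effect of 16 weeks of liraglutide. The exposure is direct because the secondary objective is itself worded as a comparison with baseline, which is the question the paired test answers.

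**Working it through.** **1. The two schedules side by side**

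| | Study Protocol, item 4 | Study Visits |
|---|---|---|
| First OGTT | screening | baseline visits, where product is handed out |
| Second OGTT | end of the 4-month intervention | repeat after 4 months |
| Relation to run-in | before | after, on the most natural reading |

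The four baseline investigations (OGTT, heparin test, kinetics, abdominal MRI), if each takes one day and is done twice, give 4 × 2 = 8. That equals the stated number of investigational visits apart from screening. It supports an OGTT outside screening, but the one-day assumption is mine.

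**2. Share of the interval that is run-in**

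From the stated durations (run-in 1 to 1.5 months, investigational phase 4 to 4.5 months):

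- total: 1 + 4 = 5 months to 1.5 + 4.5 = 6 months
- smallest share: 1 / (1 + 4.5) = 18%
- largest share: 1.5 / (1.5 + 4) = 27%

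This is a share of time, not of effect.

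**3. Effect on the paired test (illustration)**

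The plan gives no OGTT variance or run-in change, so there is no figure of its own to reproduce. From the plan: 13 completers per arm and a paired t-test. Assumed: two-sided 5% level, between-subject SD 1, visit SD s = 0.5, and a share p of subjects shifted by m during run-in, with no change during treatment.

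- bias of the mean change: p × m
- SD of the change from screening: √(2s² + p(1 − p)m²)
- standardised shift: bias / SD

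For p = 0.25, m = 0.5: bias = 0.125; SD = √(0.5 + 0.047) = 0.74; shift = 0.17. Rejection rates and ANCOVA standard error (SE) ratios are from simulation, 200,000 trials per case:

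| p | m | Bias (SD) | Standardised shift | Paired rejection, screening baseline | ANCOVA SE ratio |
|---|---|---|---|---|---|
| 0.25 | 0.5 | 0.125 | 0.17 | 8.5% | 1.05 |
| 0.25 | 1 | 0.25 | 0.30 | 16.0% | 1.18 |
| 0.5 | 0.5 | 0.25 | 0.33 | 19.7% | 1.07 |
| 0.5 | 1 | 0.5 | 0.58 | 47.7% | 1.24 |

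With the post-run-in OGTT as baseline, the paired test rejects in 5% in every case. As a cross-check, the noncentral t distribution with n = 13 gives rejection of 13% at a standardised shift of 0.25 and 38% at 0.5, which is consistent with the table.

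**4. Effect on the between-arm ANCOVA**

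Both randomised arms share the run-in, so the mean ANCOVA estimate is 0.00 and type I error is 5% in every case. The cost is precision: with a screening covariate the SE is 5% to 24% larger than with the post-run-in covariate.

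**5. Sensitivity to the visit SD**

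Paired rejection runs from 7% to 32% at s = 0.7 and from 13% to 71% at s = 0.3. Over the same range of s, the ANCOVA SE increase runs from about 2% to 56%.

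**The case against.** The best case for the plan is that Study Visits is the operational schedule and already puts the OGTT at the baseline visits, repeats it after 4 months and counts those visits apart from screening. The objectives speak of baseline, and nothing names the screening test as the analysis baseline. On this view, screening in item 4 is loose wording for the pre-treatment test, and harm requires someone to follow one phrase against the rest of the document. That lowers the weight of the point but does not remove the conflict: item 4 is the section that defines the test, and a reader who follows it does the wrong thing.

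Two limits on the reading should be stated. The figure outlining the study is not shown in the text available to me and may clarify the timing, though it could not make the two written statements agree. Also, the word that introduces the baseline visits follows the dose-escalation sentence, so placing them after run-in and before the first dose is an inference. Calling them baseline visits and handing out product there make it the better one.

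The numbers can fairly be called soft. The shares and shifts are assumed, and if no subject shifts the rejection rate is 5%. A treatment-period change of zero is also an unlikely truth, since one arm receives a glucose-lowering drug and the other is coached to lose weight. The bias of 0.125 to 0.5 SD is therefore a better guide than the rejection rates.

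**Conclusion.** The concern holds. The two sections contradict each other on when the first OGTT is done, and the plan does not say which test is the baseline. If item 4 is followed and the screening value is used, within-group OGTT changes mix run-in and treatment. Under the assumed shifts the bias is 0.125 to 0.5 between-subject SD, and paired rejection rises from 5% to between 8.5% and 47.7% at visit SD 0.5 (7% to 71% over visit SD 0.3 to 0.7).

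The consequence is conditional and confined to within-group changes in one secondary objective and the beta-cell measures modelled from the same test. The textual conflict is certain; the size of its effect is not. It should be corrected, but it does not threaten the main conclusions.

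**What to change.** Amend item 4 to agree with Study Visits, for example:

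> An OGTT will be done after an overnight fast at the baseline visits, after run-in and before the first dose of study product, and again at the end of the 4-month intervention.

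Add to Statistical Methods and Power:

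> The OGTT baseline for the paired t-test and the ANCOVA is the OGTT done at the baseline visits. A screening OGTT, if done, is not used as the baseline for change.

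The cost is wording only. Study Visits already includes an OGTT among the baseline investigations, so no visit or test is added and treatment is unchanged.
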